The dose modification instructions focus on the types of events most commonly attributed to each of the study agents. The recommendations provided in Table 6-2, and Table 6-3 comprise only guidelines; variations from these recommendations may be warranted based on an investigator's individual judgment in considering potential risks, benefits, and therapeutic alternatives available to each subject. **The exceptions are SJS/TEN or DRESS, Grade 4 ALT/AST with Bilirubin elevation, organizing pneumonia, symptomatic (Grade \geq 2) pneumonitis, PJP infection, and bowel perforation where idelalisib must be discontinued**

Table 6-2. Dose Adjustments, Withholding and Discontinuation Related to Idelalisib and/or Tirabrutinib

NCI CTCAE Grade	Recommendation	
	Idelalisib	Tirabrutinib
HEMATOLOGICAL ADVERSE EVENTS		
Neutropenia^a		
Grade ≤ 3 Neutropenia	Maintain current dose level and schedule. Blood counts must be monitored at least weekly until Grade ≤ 2.	Maintain current dose level and schedule.
Grade 4 neutropenia (or occurrence of neutropenic fever or infection)	Withhold until resolved to Grade ≤2. Consider G-CSF support. Tirabrutinib and idelalisib may be reinitiated either together or sequentially. Blood counts must be monitored at least weekly until ANC ≤ Grade 2. If the toxicity recurs, consider discontinuing idelalisib.	Withhold tirabrutinib until resolved to Grade ≤ 2. Consider G-CSF support. If the toxicity recurs, consider a decrease in tirabrutinib to 40 mg. If toxicity persists following discontinuation of idelalisib alone, discontinue tirabrutinib as well.
Thrombocytopenia		
Grade ≤ 3 Thrombocytopenia	Withhold for clinically significant bleeding.	
Grade 4 Thrombocytopenia	Withhold tirabrutinib and idelalisib until resolved to Grade 1 or baseline (recovery). Tirabrutinib and idelalisib may be reinitiated at the previous dose. If the toxicity recurs, consider a decrease in tirabrutinib to 40 mg or discontinuing tirabrutinib. If toxicity persists following discontinuation of tirabrutinib, discontinue idelalisib as well.	
NON-HEMATOLOGICAL ADVERSE EVENTS		
Rash		
Grade ≤ 2	Maintain current dose level and schedule.	
Grade 3 or 4	Withhold tirabrutinib and idelalisib until resolved to Grade 1 or baseline (recovery). Tirabrutinib and idelalisib may be resumed and a dose reduction to tirabrutinib 40 mg may be considered if multiply recurrent. If toxicity recurs following repeated rechallenge, discontinue tirabrutinib and/or idelalisib.	

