Stevens-Johnson Syndrome (SJS), Toxic Epidermal Necrolysis (TEN) and Drug Reaction with Eosinophilia and Systemic Symptoms (DRESS).		
Any Grade	Discontinue Idelalisib and concomitant medications that have been associated with SJS/TEN and drug reaction with eosinophilia and systemic symptoms (DRESS). Institute systemic immunosuppression per institutional standards.	-

NCI CTCAE Grade	Recommendation	
	Idelalisib	Tirabrutinib
Bowel Perforation		
Any Grade	Discontinue idelalisib.	Maintain current dose level and schedule.
Progressive Multifocal Leukoencephalopathy (PML)		
Any Grade	Withhold idelalisib until PML is excluded. Refer to section 6.6.11	-
Diarrhea		
Grade \geq 1	In the absence of evidence of infection, provide anti-diarrheal (eg, loperamide) and maintain current tirabrutinib and idelalisib dose level and schedule.	
Grade 2	Withhold idelalisib until Grade \leq 1. Consider anti-diarrheal (eg, loperamide). Resume idelalisib at previous dose level. If rechallenge results in recurrence, discontinue idelalisib. Consider addition of anti-inflammatory (eg, budesonide).	Withhold tirabrutinib until resolved to Grade \leq 1. If resolution occurs within 7 days, tirabrutinib may be reinitiated at the previous dose. If the toxicity recurs or is persistent with corticosteroid therapy, decrease to 40 mg.
Grade 3 or 4	Withhold idelalisib until resolved to Grade 1 or baseline (recovery). Rule out infectious etiology including CMV (see Section 6.2.10.1). Consider anti-diarrheal (eg, loperamide) and/or addition of anti-inflammatory agent (eg, sulfasalazine, budesonide). If toxicity persists or recurs upon repeated rechallenge, permanently discontinue idelalisib. Refer to Section 6.2.10.1 for evaluation.	Withhold tirabrutinib until Grade \leq 1. Consider anti-diarrheal (eg, loperamide) and/or addition of anti-inflammatory agent (eg, sulfasalazine, budesonide).
Hepatic Adverse Events (elevations in ALT, AST or bilirubin)		
Grade 1 (ALT/AST \leq 3 \times ULN) (Bilirubin \leq 1.5 \times ULN)	Maintain current dose level and schedule.	
Grade 2 (ALT/AST > 3-5 \times ULN) (Bilirubin > 1.5 - \leq 3 \times ULN)	Maintain current dose level and schedule. Monitor ALT, AST, ALP, and bilirubin at least 1 \times per week.	

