Grade 3 (ALT/AST > 5-20 \times ULN) (Bilirubin > 3-10 \times ULN)	Withhold all study medication. Monitor ALT, AST, ALP, and bilirubin at least 1 \times per week until all abnormalities are Grade \leq 1 or baseline. If bilirubin abnormality was Grade < 3, resume tirabrutinib and idelalisib at previous dose level and resume obinutuzumab. If bilirubin abnormality was Grade \geq 3, discontinue idelalisib and obinutuzumab.	
Grade 4 (ALT/AST > 20 \times ULN) (Bilirubin > 10 \times ULN)	Withhold all study medication. Monitor ALT, AST, ALP, and bilirubin at least 1 \times per week until all abnormalities are Grade \leq 1 or baseline. If bilirubin abnormality was Grade < 3, resume tirabrutinib only. If bilirubin was Grade 4, discontinue all study medication.	

NCI CTCAE Grade	Recommendation	
	Idelalisib	Tirabrutinib
Organizing Pneumonia		
Any Grade	Discontinue idelalisib permanently. Institute supportive care as appropriate.	
Pneumonitis		
Grade 1	Withhold all study medication until resolution to baseline. May resume therapy at investigator discretion.	
Grade 2	Discontinue all study medication. Supportive care, including oxygen or mechanical ventilation, should be considered early and provided as necessary. May consider resuming therapy with tirabrutinib alone after discussion with medical monitor.	
Grade 3 or 4	Discontinue all study medication permanently, institute systemic corticosteroids and supportive care per institutional standard.	
PJP infection		
Any Grade	Discontinue idelalisib. Consider discontinuation of tirabrutinib until the infection has resolved.	
Unequivocal CMV infection^a		
Any Grade	Discontinue idelalisib. Consider discontinuation of tirabrutinib until the infection has resolved. If the benefits of resuming idelalisib are judged to outweigh the risks, consideration should be given to administering pre-emptive CMV therapy.	
Hypersensitivity		
Any Grade	Consider interrupting or discontinuing tirabrutinib treatment (see Section 6.6.2).	
OTHER NON-HEMATOLOGICAL ADVERSE EVENTS		
Grade 1	Maintain current dose level and schedule	
Grade 2	Withhold tirabrutinib and idelalisib until Grade \leq 1 or baseline. May resume idelalisib with tirabrutinib at initial or lower dose level or discontinue tirabrutinib and idelalisib at investigator discretion.	
Grade 3	Withhold tirabrutinib and idelalisib until Grade \leq 1 or baseline. May resume idelalisib with tirabrutinib at lower dose level or discontinue tirabrutinib and idelalisib at investigator discretion.	

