Grade 4	Delay all study medication until subject is sufficiently stable to receive further treatment; if recurrent with rechallenge, consider treatment with tirabrutinib alone.

NCI CTCAE Grade	Recommendation
	Toxicity attributable to obinutuzumab
Hepatic Adverse Events (elevations in ALT, AST, or bilirubin)	
Grade ≤1 (ALT/AST≤3×ULN) (Bilirubin≤1.5×ULN)	Maintain current dose level and schedule.
Grade 2 (ALT/AST>3-5×ULN) (Bilirubin>1.5-≤3×ULN)	Maintain current dose level and schedule.
Grade 3 (ALT/AST>5-20×ULN) (Bilirubin>3-10×ULN)	Withhold all study medication. Monitor ALT, AST, ALP, and bilirubin at least 1× per week until all abnormalities are Grade ≤ 1 or baseline. If bilirubin abnormality was Grade < 3, resume tirabrutinib and idelalisib at previous dose level, resume obinutuzumab. If bilirubin abnormality was Grade ≥ 3, discontinue idelalisib and obinutuzumab.
Grade 4 (ALT/AST>20×ULN) (Bilirubin>10×ULN)	Withhold all study medication. Monitor ALT, AST, ALP, and bilirubin at least 1× per week until all abnormalities are Grade ≤ 1 or baseline. If bilirubin abnormality was Grade < 3, resume tirabrutinib. If bilirubin was grade 4, discontinue all study medication.
Pneumonitis	
Grade ≤1	Maintain current dose level and schedule.
Grade 2	Withhold all study medication until Grade ≤ 1, consider systemic corticosteroids. May consider resuming therapy with tirabrutinib alone
Grade ≥3	Delay obinutuzumab as necessary to ensure subject is sufficiently stable to receive further treatment; thereafter maintain full dose and schedule or discontinue obinutuzumab at investigator discretion.
Hypersensitivity	
Any Grade	Stop the infusion and discontinue obinutuzumab treatment (see section 6.6.2)
OTHER NON-HEMATOLOGICAL ADVERSE EVENTS	
Grade ≤2	Maintain current dose level and schedule.
Grade ≥3	If felt to be related to obinutuzumab, delay obinutuzumab as necessary to ensure subject is sufficiently stable to receive further treatment; thereafter maintain full dose and schedule or discontinue obinutuzumab at investigator discretion.

Abbreviations: ALP alkaline phosphatase, ALT alanine aminotransferase, AST aspartate aminotransferase, ANC absolute neutrophil count, CTCAE Common Terminology Criteria for Adverse Events, G CSF granulocyte colony stimulating factor, NCI National Cancer Institute, ULN upper limit of normal

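### Protocol Tables 6-2 and 6-3 have no Grade 4-row branch for ALT/AST Grade 4 with bilirubin Grade 3, and their rows differ on tirabrutinib for ALT/AST Grade 3 with bilirubin Grade 4

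*Protocol*

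**What the plan says.** The hepatic block of Protocol Table 6-2 is headed "Hepatic Adverse Events (elevations in ALT, AST or bilirubin", and each row lists both an ALT/AST range and a bilirubin range. Grade 3 is ALT/AST above 5 to 20 times ULN and bilirubin above 3 to 10 times ULN. Grade 4 is ALT/AST above 20 times and bilirubin above 10 times ULN. In both rows every study drug is held and liver tests are repeated at least weekly until all abnormalities are back to Grade 1 or lower, or to baseline. The next step depends on bilirubin:

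- **Grade 3 row, bilirubin below Grade 3:** "resume tirabrutinib and idelalisib at previous dose level and resume obinutuzumab".
- **Grade 3 row, bilirubin Grade 3 or higher:** "discontinue idelalisib and obinutuzumab". Tirabrutinib is not mentioned.
- **Grade 4 row:** "If bilirubin abnormality was Grade < 3, resume tirabrutinib only. If bilirubin was Grade 4, discontinue all study medication". Bilirubin Grade 3 is not mentioned.

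Table 6-3 has the same structure. Its Grade 4 row reads "If bilirubin abnormality was Grade < 3, resume tirabrutinib. If bilirubin was grade 4, discontinue all study medication".

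The text of Section 6.5 calls both tables guidelines from which investigators may depart, but lists exceptions where idelalisib must be stopped. One of these is "Grade 4 ALT/AST with Bilirubin elevation, organizing pneumonia" (the quote runs on into the next item of the list). That sentence says nothing about tirabrutinib or obinutuzumab.

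**The concern.** A table entered on either of two markers needs a branch for each pair of grades, or a rule for pairs whose grades differ. These tables have neither for two pairs in which both markers are severely raised. After the same laboratory course and recovery, one site could restart tirabrutinib and another could stop it permanently, and each could point to the table.

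The main stake is safety: whether a subject is re-exposed after a combined transaminase and bilirubin rise would depend on which row the site reads. Differing grades are foreseeable, since Protocol Section 6.6.3 itself describes bilirubin rising disproportionately to transaminases.

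The second stake is reporting. The SAP tabulates completion status by drug (Section 4.1) and adverse events leading to discontinuation of each drug (Section 7.1.6.1), so those counts would partly reflect the reading chosen.

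**Working it through.** No sample size, power or event figure is involved. The check is an enumeration of grade pairs against the Grade 3 and Grade 4 rows of Table 6-2. T is tirabrutinib, I idelalisib and O obinutuzumab. In every line all drugs have already been held.

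| ALT/AST grade | Bilirubin grade | Grade 3 row | Grade 4 row | Left open by the rows |
|---|---|---|---|---|
| 3 | below 3 | resume T, I, O | not entered | nothing |
| 3 | 3 | stop I, O; T not mentioned | not entered | T after the hold |
| 3 | 4 | stop I, O; T not mentioned | stop all | T: silence against a stop |
| 4 | below 3 | not entered | resume T only | nothing in Table 6-2 |
| 4 | 3 | stop I, O; T not mentioned (if entered through bilirubin) | no branch | T; also O if only the Grade 4 row is read |
| 4 | 4 | not entered | stop all | nothing |

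**Full grid.** Pairs of grades 0 to 4 with at least one marker at Grade 3 or 4: 2 × 5 = 10 with ALT/AST at Grade 3 or 4, plus 3 × 2 = 6 with ALT/AST at Grade 0 to 2 and bilirubin at Grade 3 or 4. The total is 16. I assume that a marker at Grade 3 or 4 takes the subject out of the Grade 1 and 2 rows.

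- **One explicit outcome, 10 pairs:** bilirubin Grade 4 with ALT/AST Grade 0, 1 or 2 (3); ALT/AST Grade 3 with bilirubin below 3 (3); ALT/AST Grade 4 with bilirubin below 3 (3); Grade 4 on both (1).
- **One outcome, silent on tirabrutinib, 4 pairs:** bilirubin Grade 3 with ALT/AST Grade 0, 1, 2 or 3.
- **No single consistent outcome, 2 pairs:** ALT/AST 4 with bilirubin 3, and ALT/AST 3 with bilirubin 4.

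10 + 4 + 2 = 16.

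**Does a row-priority rule rescue it?** None is stated. If the worst grade governs, the second pair becomes stop all, but the first still has no branch. If ALT/AST grade governs, the first still has no branch, and the second falls to the Grade 3 row, which is silent on tirabrutinib. If every matching row applies, obinutuzumab is settled for the first pair, tirabrutinib is not, and the second pair has two row outcomes. The Grade 3 row's reference to bilirubin of Grade 3 or higher also counts against a worst-grade rule, under which bilirubin Grade 4 would never reach that row.

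**Does another section settle it?**

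- The mandatory list in Section 6.5 settles idelalisib for ALT/AST Grade 4 with raised bilirubin.
- Section 7.5 sends the reader to Section 6.4 for dose modifications. Section 6.4 points to Sections 3.4 and 3.5, and Section 3.4 points back to Section 6.5.
- Section 6.6.4 covers transaminase rises and HBV reactivation, not combined bilirubin elevation.
- Table 6-3 repeats both features. It also omits the word restricting resumption to tirabrutinib, so it adds a small difference and resolves nothing.

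**Effect on a table.** With about 30 subjects in Arm B, one subject classified differently moves a tirabrutinib discontinuation rate by 1/30, or 3.3 percentage points.

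**The case against.** The strongest reply is that the practical gap is small and that sites have a route through it. Both rows hold every drug at once, so no reading continues treatment through the acute event. For ALT/AST Grade 3 with bilirubin Grade 4, the rows agree on idelalisib and obinutuzumab, and the Grade 3 row does not say to resume tirabrutinib; it is only silent. For ALT/AST Grade 4 with bilirubin Grade 3, entering the Grade 3 row through its bilirubin range stops obinutuzumab, and Section 6.5 stops idelalisib. The tables are guidelines. Section 6.5 generally bars further doses of an interrupted oral drug if toxicity has not improved to Grade 2 or lower within 2 weeks, and sends longer events to case-by-case review. Section 7.5 directs questions to the medical monitor.

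Most of this stands, and it narrows the point largely to tirabrutinib. It does not remove it. Freedom to depart from a recommendation neither supplies a missing one nor chooses between two. The 2-week provision does not help with a subject who recovers promptly.

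A reader might also infer from the 31% and 25% rates of Grade 3 or higher ALT and AST rises in Protocol Section 1.4 that these pairs will be common. The documents do not support that. Those 32 subjects were previously untreated and received idelalisib 150 mg twice daily, against 100 mg once daily here, and no joint bilirubin frequency is reported.

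**Conclusion.** The hepatic rows are wrong as written: an internal inconsistency affecting 2 of 16 grade pairs.

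- **ALT/AST Grade 4 with bilirubin Grade 3:** tirabrutinib is undetermined, and obinutuzumab too if only the Grade 4 row is read.
- **ALT/AST Grade 3 with bilirubin Grade 4:** the rows differ on tirabrutinib alone, with no rule of precedence.

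Only resumption versus permanent discontinuation is at issue. The count rests on the assumption stated above about the Grade 1 and 2 rows. The frequency of the two pairs is not given.

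A reader might infer that sites cannot apply the tables to the most severe liver signal. That is not supported, because Grade 4 on both markers has one explicit outcome in both tables. Nor should SAP Section 7.2.3 be read as describing the affected group: it counts AST or ALT above 3 times ULN with bilirubin above 1.5 or 2 times ULN, which is much broader. No effect on the Week 25 CR analysis is shown. The point still merits correction, because a stopping rule for combined severe liver abnormalities should not give two answers or none.

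**What to change.** Reconcile the hepatic rows of Tables 6-2 and 6-3 with each other and with the mandatory-discontinuation sentence in Section 6.5. Each combination of ALT/AST grade and bilirubin grade should give one instruction per study drug, and the text should state which row governs when the two grades differ. The sponsor decides the clinical content; none is proposed here. The cost is amendment wording or a clarification letter to sites, with no new data or visits.

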Grade 4	Discontinue tirabrutinib and idelalisib.	

a) CMV should be diagnosed using clinical or laboratory criteria per established institutional standard

Table 6-3. Dose Adjustment Guidelines for Subjects Receiving Obinutuzumab

NCI CTCAE Grade	Recommendation
	Toxicity attributable to obinutuzumab
HEMATOLOGICAL ADVERSE EVENTS*	
Neutropenia^a	
Grade ≤ 2 neutropenia	Maintain current dose level and schedule.
Grade 3 neutropenia	Maintain current dose level and schedule. Consider G-CSF support.
Grade 4 neutropenia (or occurrence of neutropenic fever or infection)	Delay obinutuzumab until Grade ≤ 2 (ANC ≥ 1 × 10 ⁹ /L) and/or neutropenic fever or infection is resolved; thereafter, resume at full dose. Consider G-CSF support to avoid delays. If delay is > 4 weeks, discontinue obinutuzumab.
Thrombocytopenia	
Grade ≤3	Maintain current dose level and schedule.
Grade 4	Delay obinutuzumab until Grade ≤ 3 (platelets ≥ 25 × 10 ⁹ /L); thereafter, resume at full dose. If delay is > 4 weeks, discontinue obinutuzumab, unless the Grade 4 thrombocytopenia occurred after the first 3 weekly doses.
Hemorrhage	
N/A	
Hold obinutuzumab in case of platelets < 20,000/μL. If Day 8 is delayed then skip Day 8 and administer Day 15 as previously scheduled (if symptomatic bleeding has resolved). If Day 15 is delayed then skip Day 15 dosing and administer Day 29 of obinutuzumab as scheduled.
 
At the discretion of the study investigator, for subjects who are on low molecular weight heparin (LMWH), when thrombocytopenia with platelets <20,000/μL develops, reduce the dose of LMWH or new oral anticoagulants (NOAC) used.
 
Hold tirabrutinib and obinutuzumab for clinically significant bleeding (irrespective of platelet count) until it resolves.

NON-HEMATOLOGICAL ADVERSE EVENTS	
Cutaneous	
Grade ≤2	Maintain current dose level and schedule.
Grade 3 or 4	Delay obinutuzumab until Grade ≤ 1; thereafter, may resume at full dose or discontinue obinutuzumab at investigator discretion.
Gastrointestinal Inflammation/Diarrhea	
Grade ≤1	Maintain current dose level and schedule.
Grade 2	Maintain current dose level and schedule.
Grade 3	Hold idelalisib and obinutuzumab until subject is sufficiently stable to receive further treatment; thereafter maintain full dose and schedule. If recurrent with rechallenge, consider treatment with tirabrutinib alone.

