6.6.6. Infectious Events

Patients with lymphoid cancers receiving tirabrutinib, idelalisib or obinutuzumab have developed serious and fatal infections during therapy. Opportunistic infections, most notably *Pneumocystis jirovecii* pneumonia (PJP) and CMV infection, have most frequently occurred within the first 6 months of treatment with idelalisib and are increased in the context of concurrent myelosuppressive therapy such as bendamustine.

Subjects must receive trimethoprim-sulfamethoxazole or other established prophylaxis for PJP throughout the course of idelalisib treatment. Prophylaxis will continue for a period of 2 to 6 months after the last dose of idelalisib. The duration of prophylaxis should be based on clinical judgment of the investigator and may take into account risk factors such as concomitant corticosteroid treatment and prolonged neutropenia after idelalisib treatment ends.

CMV surveillance for active disease (quantitative PCR or PP65 antigen) must be conducted approximately every 4 weeks through week 33 and every 12 weeks thereafter through the course of idelalisib treatment. CMV viral load testing should be performed from the same specimen type whenever possible and caution should be exercised when comparing CMV viral load results across different testing centers. If unequivocal clinical or laboratory evidence of CMV infection is present, the subject must permanently discontinue idelalisib treatment and undergo effective antiviral treatment according to established clinical guidelines.

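### The protocol contradicts itself on idelalisib after unequivocal CMV infection: Section 6.6.6 requires permanent discontinuation, while Table 6-2 provides for resuming it

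*Protocol*

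**What the plan says.** Section 6.6.6 (Infectious Events) reads: "If unequivocal clinical or laboratory evidence of CMV infection is present, the subject must permanently discontinue idelalisib treatment". It adds antiviral treatment and makes no provision for a restart. The same section reports serious and fatal infections with the study drugs. It says that PJP and "CMV infection, have most frequently occurred within the first 6 months of treatment with idelalisib", and it requires CMV surveillance throughout idelalisib treatment.

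Table 6-2 in Section 6.5 has a row for unequivocal CMV infection at any grade. It tells the site to discontinue idelalisib and to consider stopping tirabrutinib until the infection resolves. It then says: "If the benefits of resuming idelalisib are judged to outweigh the risks, consideration should be given to administering pre-emptive CMV therapy". Footnote a to the table adds: "CMV should be diagnosed using clinical or laboratory criteria per established institutional standard".

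The text of Section 6.5 bears on this in three places:

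- Tables 6-2 and 6-3 "comprise only guidelines; variations from these recommendations may be warranted".
- The exceptions to that latitude are a list of events ending with "PJP infection, and bowel perforation where idelalisib must be discontinued". CMV infection is not on the list.
- The general text on interruptions says that when toxicity is put down to one oral agent, the agent that was discontinued is not to be restarted on study. A later paragraph says that an AE lasting more than 2 weeks is reviewed case by case by investigator and sponsor. Either oral drug may then continue if this is consistent with Table 6-2.

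**The concern.** An investigator with a confirmed CMV infection can turn to either passage. One rules out any further idelalisib. The other describes the conditions under which it may be given again. Nothing in the protocol says which passage takes precedence.

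Two things are at stake. The first is patient safety: the protocol itself treats CMV as one of the notable opportunistic infections with idelalisib, and the instruction for that event should not depend on which page the site reads. The second is the record of conduct. Protocol Section 6 asks investigators to document every deviation, and SAP Section 4.3 tabulates important deviations by reason. A restart after CMV infection is a deviation if judged against Section 6.6.6 and is not one if judged against Table 6-2. Safety and tolerability is the secondary objective, so this record matters to the report.

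**Working it through.** No arithmetic applies. The check is whether the two passages address the same case, and whether any other text decides between them.

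1. **Same drug.** Both passages instruct on idelalisib.

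2. **Same trigger.** Section 6.6.6 requires unequivocal evidence, clinical or laboratory. The Table 6-2 row is labelled unequivocal CMV infection, covers any grade, and through footnote a relies on clinical or laboratory criteria. Neither grade nor type of evidence separates them.

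3. **Same status.** Both are current protocol text, not entries in a summary of changes.

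4. **What each passage makes of a site's conduct:**

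| What the site does | Under Section 6.6.6 | Under the Table 6-2 CMV row |
|---|---|---|
| Stops idelalisib and never restarts | Complies | Complies |
| Stops, then resumes on a benefit-risk judgment | Breach | Provided for |

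The passages part only in the second line, but there they are incompatible.

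5. **Does Section 6.5 decide it?**
 - *The guidelines sentence* names Tables 6-2 and 6-3 only. It gives latitude around the table and does not soften the mandatory wording of Section 6.6.6.
 - *The list of mandatory discontinuations* includes PJP and omits CMV. That leaves the table's discretion in place for CMV and does nothing to enforce Section 6.6.6.
 - *The re-initiation text* points both ways. The rule against restarting an agent stopped for its own toxicity supports Section 6.6.6, although it appears in the context of toxicity that has not resolved within 2 weeks. The case-by-case paragraph refers back to Table 6-2, which is the text that provides for resumption.

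6. **Effect on the analysis.** The primary analysis is the Week 25 CR rate with a 90% Clopper-Pearson interval and 30 subjects planned for Arm B. None of these inputs depends on the CMV instruction.

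**The case against.** The best case for the protocol is that the conflict runs in one direction only. Table 6-2 also starts with discontinuation and never requires a restart, so a cautious site meets both texts. A reader could also rank them, since one is mandatory and the other is described as guidance. Protocol Section 7.5 sends questions on toxicity management to the medical monitor, who could keep handling uniform. The asymmetry is real, and the monitor reduces the risk in practice. But the ranking is nowhere stated, and Section 6.6.6 itself sits under a Section 6.6 heading that speaks of recommendations. None of this removes the sentence that provides for resumption.

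Several stronger readings are tempting and are not supported:

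- *That Section 6.5 as a whole sides with the table.* The omission of CMV from the mandatory list suggests this, but the rule against re-initiation in the same section points the other way.
- *That the table signals a temporary stop by leaving out the word permanently.* The organizing pneumonia row does say "Discontinue idelalisib permanently. Institute supportive care as appropriate". But the rows for SJS/TEN/DRESS, bowel perforation and PJP also lack the word, and all three are on the mandatory list. Only the resumption sentence carries weight.
- *That the surveillance schedule measures the size of the problem.* Testing "must be conducted approximately every 4 weeks through week 33 and every 12 weeks thereafter" gives 8 scheduled tests after Week 1 (Weeks 5 to 33, every 4 weeks) plus 5 (Weeks 45, 57, 69, 81, 93), or 13 in 104 weeks of treatment. That counts tests, not infections, and a scheduled test is not an unequivocal infection.
- *That the SAP's per-drug tables would misclassify cases.* SAP Section 7.1.6.1 separates discontinuation from temporary interruption of idelalisib. If one subject stops and another resumes, those tables correctly record what each did. The ambiguity lies in deviation status.
- *That bowel perforation and pneumonitis are contradictions of equal weight.* They are not, as set out in the verdict.

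**Conclusion.** The contradiction stands on the current text and should be corrected: for the same drug and event, one passage forbids resumption and another provides for it. It matters because it concerns a stopping rule for a serious infection, not because it moves any result. Only subjects with unequivocal CMV infection are affected. The documents give no CMV event rate for this three-drug regimen at these doses, so no number of subjects is claimed. No efficacy estimate or confidence interval changes. The conclusion rests on reading the two passages as applying to the same infection, which the shared wording of the trigger supports.

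Two minor points nearby deserve a note and add nothing to the weight of this one:

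- *Bowel perforation.* All texts agree on stopping idelalisib. Section 6.6.3 discontinues study treatment without naming drugs, while Table 6-2 keeps tirabrutinib unchanged. Section 6.6.3 also says that rituximab may be resumed after recovery from severe abdominal pain, yet rituximab is not a study drug. Table 6-3 has no perforation row, but its row for other non-hematological events partly covers obinutuzumab.
- *Pneumonitis.* Tables 6-2 and 6-3 differ at Grade 1, at Grade 2 and at Grade 3 or higher, and Table 6-2 speaks of all study medication. The tables are largely separated by the drug to which the event is attributed. Section 6.5 gives the investigator discretion over a drug not held responsible. At Grade 2 both tables allow tirabrutinib alone to be considered. What stays open is obinutuzumab when attribution is shared or uncertain.

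**What to change.** The sponsor's clinical team should reconcile four texts so that one instruction on idelalisib after CMV infection remains: Section 6.6.6, the CMV row of Table 6-2, the list of mandatory discontinuations in Section 6.5, and the re-initiation text in the same section. Sites should then be notified. This review does not say which rule is right.

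In the same revision:

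- reconcile Section 6.6.3 with Table 6-2 on bowel perforation by naming the drugs meant, and correct or explain the rituximab sentence;
- state how the pneumonitis rows of Tables 6-2 and 6-3 apply to obinutuzumab when attribution is shared or uncertain.

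The cost is protocol wording and a site letter, with no extra subjects or procedures. If dosing has already ended, the remaining step is a documented rule, set before reporting, on whether any resumption of idelalisib after CMV infection counts as a deviation under SAP Section 4.3.

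### Protocol Table 6-3 gives two platelet triggers for withholding obinutuzumab and, for Days 8 and 15 only, two ways to handle the held dose, without saying which governs

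*Protocol*

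**What the plan says.** All the text at issue is in Protocol Section 6.5, Table 6-3.

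- **Thrombocytopenia row.** At Grade 3 or lower the schedule is kept. At Grade 4: "Delay obinutuzumab until Grade ≤ 3 (platelets ≥ 25 × 10 ⁹ /L); thereafter, resume at full dose". A limit follows: "If delay is > 4 weeks, discontinue obinutuzumab, unless the Grade 4 thrombocytopenia occurred after the first 3 weekly doses".
- **Hemorrhage row.** It opens with a platelet rule, "Hold obinutuzumab in case of platelets", with the limit set at below 20,000/µL. For the two weekly doses after the first it says "If Day 8 is delayed then skip Day 8 and administer Day 15 as previously scheduled (if symptomatic bleeding has resolved"), and then "If Day 15 is delayed then skip Day 15 dosing and administer Day 29 of obinutuzumab as scheduled". A separate sentence covers bleeding: "Hold tirabrutinib and obinutuzumab for clinically significant bleeding (irrespective of platelet count) until it resolves".

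Three other places bear on the point. Section 5.3.2 allows repeat infusions to be delayed for recovery and mentions no skipping. Section 6.5 describes Tables 6-2 and 6-3 as guidelines that the investigator may vary. Footnote a to Table 6-3 says thrombocytopenia thought to be due to CLL need not delay obinutuzumab. None of these says which row prevails.

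**The concern.** A site with a thrombocytopenic Arm B subject finds two instructions in the same table. They differ in the count that triggers a hold, in the condition for giving the next dose, and in whether a held Day 8 or Day 15 dose is given late or dropped. Two sites following the text faithfully could act differently on the same count.

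At stake are the safety of dosing at a very low platelet count and the number of infusions received. The second reaches the report, because SAP Section 4.2.1 summarises the number of obinutuzumab infusions. The Thrombocytopenia row also carries a discontinuation limit, so whether a subject must stop obinutuzumab could depend on which row was followed.

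**Working it through.** The documents give no figure to reproduce. The check puts both thresholds in one unit and applies both rows to the same cases.

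**Units.** 25 × 10⁹/L ÷ 10⁶ µL/L = 25,000/µL, against 20,000/µL in the Hemorrhage row. The difference is 25,000 − 20,000 = 5,000/µL.

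**Trigger.**

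| Platelets (/µL) | Thrombocytopenia row | Hemorrhage row, platelet rule |
|---|---|---|
| 15,000 | delay | hold |
| 19,999 | delay | hold |
| 20,000 | delay | not triggered |
| 22,000 | delay | not triggered |
| 24,999 | delay | not triggered |
| 25,000 | keep schedule | not triggered |

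The thresholds are nested: every count below 20,000 is also below 25,000. The triggers differ only from 20,000 to 24,999/µL.

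**Schedule.** Appendix 2, note 6, gives Days 1, 8 and 15, then Weeks 5, 9, 13, 17 and 21. Day 1 of Week w is study day 7(w − 1) + 1, so the later doses fall on Days 29, 57, 85, 113 and 141. That makes 3 + 5 = 8 doses.

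**Three cases, none with bleeding.**

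1. *Day 8 held at 15,000/µL; 22,000/µL on Day 15.* The Thrombocytopenia row still delays, because 22,000 < 25,000. In the Hemorrhage row the platelet hold no longer applies, and the instruction is to give Day 15 on its planned date. The actions differ.
2. *Day 8 held at 15,000/µL; above 25,000/µL on Day 11.* The Thrombocytopenia row allows resumption from Day 11. The Hemorrhage row drops Day 8 and waits for Day 15. The actions differ.
3. *Day 8 held at 15,000/µL; still 15,000/µL on Day 15.* Both rows withhold Day 15. The actions agree.

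**Dose count.** If a held dose is given late, 8 doses remain possible. Skipping one leaves 8 − 1 = 7; skipping both leaves 8 − 2 = 6. From Day 29 on only the delay rule exists, so the other doses carry no missed-dose conflict.

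**The 4-week limit.** The exception is for Grade 4 events arising after the first three weekly doses, so the limit applies in the early period that the skip rule also covers. Counted from a held Day 8 dose, four weeks end on Day 8 + 28 = 36. If skipped doses do not count as delays and Day 29 is the first dose actually delayed, they end on Day 29 + 28 = 57. The table does not say which count is meant.

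**The case against.** The strongest reply is that the rows can be read together. The thresholds are nested, so a site that follows the Thrombocytopenia row breaches no hold in the Hemorrhage row, which is silent at 20,000 to 24,999/µL and does not tell the site to ignore the count. The Thrombocytopenia row does not expressly require a missed dose to be made up, and Section 3.3 provides for up to 8 doses. One could therefore hold until recovery, not make up Day 8 or Day 15, and resume at the next planned infusion. The tables are guidelines, and footnote a relaxes delay for CLL-related cytopenia.

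Much of this stands and narrows the point. The combined reading is possible, but the table does not state it, and in cases 1 and 2 each row taken as written leads elsewhere. Guideline status lets an investigator depart from a default but does not say which of two defaults applies.

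Another reply is that the Hemorrhage row concerns only bleeding subjects. Its first sentence is triggered by platelets alone, and its last already holds for significant bleeding at any count, so on that reading the 20,000/µL figure would have little function of its own.

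A reader might also go too far the other way and infer that the Hemorrhage row lets a subject still below 20,000/µL be dosed on Day 15 once any bleeding has resolved. The documents do not support that. The hold below 20,000/µL is not limited to Day 8, and the row itself provides for Day 15 being delayed.

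**Conclusion.** The point holds with a narrow scope. The rows agree below 20,000/µL. They conflict on the trigger and recovery condition across a band of 5,000/µL, and on the missed dose for two of the eight planned infusions, with 8, 7 or 6 doses possible. How the 4-week limit applies to a skipped dose is unstated.

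The 8-dose end of the range assumes that resuming means giving the held dose late, which the Thrombocytopenia row permits but does not require. The documents give no frequency for such counts and no relation between infusions received and response, so no shift in the Week 25 CR rate can be derived. It would be tempting to infer a bias in the primary result; the documents do not show one, and subjects with fewer infusions remain in the Full Analysis Set. This is a contradiction in dosing instructions that bears on safety and exposure and should be corrected; it does not undermine the primary analysis.

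**What to change.** The sponsor should reconcile the Thrombocytopenia and Hemorrhage rows of Table 6-3 so that one hold trigger, one recovery condition and one missed-dose rule apply to Days 8 and 15. The text should also say whether the 4-week limit runs when a dose is skipped and from which dose it is counted. If the Hemorrhage row is meant only for bleeding subjects, it should say so. Which threshold and which rule apply is for the sponsor to decide.

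The cost is a clarification of one protocol table and notice to sites. The SAP needs no change, since its exposure summary counts the infusions given under either rule.
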